4.2 SAFETY ANALYSIS

The safety analysis is the same as the full analysis.

4.3 OTHER ANALYSIS

NA

4.4 SUBGROUPS

NA

5 OBJECTIVES AND VARIABLES

The primary objective of the study is *to identify patients with metastatic renal cell carcinoma (mRCC) who obtained a complete response (CR) to treatment with Sunitinib exclusively or with Sunitinib and a local treatment to eliminate residual disease in the opinion of the clinician. Complete response (CR) is defined as the disappearance of all measurable lesions according to the investigator's criterion in at least 2 consecutive CT scans.*

The clinical baseline characteristics of these patients and the tumour will be described in order to look for predictive response factors.

[figure not shown]
The intention is to describe the therapeutic strategy used in patients who obtained the greatest clinical benefit in the cases described once the macroscopic lesions were eradicated in order to draft recommendations to be followed once the registry's statistical analysis is available.

The variables to be analysed for this study will be obtained from the patients' medical records and case report forms according to the protocol. The data will be recorded on the paper CRF designed for this study where the following patient information will be included:

DEMOGRAPHIC AND DISEASE INFORMATION

- 1) Age at the start of treatment for metastatic disease
- 2) Functional status, measured by the ECOG scale (0, 1, 2, 3, 4) and/or by means of the KPS (Karnofsky Performance Status) scale, at the start of treatment (see annex I)
- 3) Motzer and Heng prognostic criteria
- 4) Laboratory data (haemoglobin, leukocytes, corrected calcium, LDH levels, lymphocytes, platelets, neutrophils, lymphocytes)
- 5) Comorbidities
- 6) Date the disease was diagnosed
- 7) Metastasis site(s) and number
- 8) Furhrman grade (I, II, III, IV)

PFIZER CONFIDENTIAL

- 9) Tumour stage (TNM)
- 10) Previous nephrectomy
- 11) Necrosis

TREATMENT

- 1) Start date of treatment with first-line Sunitinib
- 2) Initial dose and treatment regimen
- 3) Type of treatment received (monotherapy or in combination with local treatment) and technique used in the case of local treatment
- 4) Response to treatment.
- 5) Date of completion of the treatment after CR if treatment is interrupted
- 6) Modification of dosage and/or treatment regimen, number of changes in the dose, reason, date and new dose
- 7) Dose interruptions, number of interruptions, reason, date of interruption and restart and new dose

CCI

- 9) Adverse reactions

POST-TREATMENT

- 1) Continuation of treatment in 1st line
- 2) End date and reason
- 3) Date of progression
- 4) Date of and reason for death
- 5) Post-Sunitinib treatments (another TKI, mTOR, immunotherapy)

The following aspects will be assessed using the variables collected:

- **Time from nephrectomy to the start of systemic treatment:** defined as the time interval from the day of the nephrectomy to the day treatment with Sunitinib started.
- **Time to CR:** defined as the time interval from the day treatment with Sunitinib started until the day the complete response is documented in the first CT scan without lesions.
- **Duration of treatment with Sunitinib once CR is reached:** defined as the time interval from the day on which the complete response is documented until the day that the definitive discontinuation of the treatment is confirmed, either at the patient's own decision or at the doctor's decision.
- **Time to progression (TTP):** defined as the time interval from the day on which the complete response is documented until the first day that objective tumour progression, if any, is observed.
- **Time to change of treatment:** in patients who continue treatment with Sunitinib once the lesions have disappeared, it is defined as the time interval from the day on which the complete response is documented until the first day on which the change of treatment due to unacceptable toxicity is documented, as applicable.
- **Time to death:** defined as the time interval from the day on which the

Pfizer Confidential

complete response is documented to the day on which death from any cause is documented, if it occurs.

- **Duration of complete response (DOR):** defined as the time interval from the date on which the complete response to Sunitinib is identified until the date of the CT scan conforming tumour progression, the change of treatment due to unacceptable toxicity, death from any cause or until the date of the last follow-up at the close of the study. It represents the time that the patient survives without signs of disease.

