1. LIST OF ABBREVIATIONS

Abbreviation	Definition
AE	Adverse Event
AEM	Adverse event monitoring
AEMPS	Agencia Española de Medicamentos y Productos Sanitarios (Spanish Agency of Medicines and Medical Devices)
AR	Autonomous Regions
AUC	Area under the curve
	Heng risk criteria for anti-VEGF targeted therapies; Prognostic Factors for poor Overall Survival: KPS <80 Time from diagnosis to start of treatment <1 year Anaemia Hypercalcaemia Neutrophilia Thrombocytosis 0 Factors: favourable prognosis group 1-2 Factors: intermediate prognostic group ≥3 Factors: poor prognostic group.
Classification of the prognostic group according to Heng	
Continuous CR	Continuous CR with no changes in the last recorded imaging test

	(CT).
CR	Complete Response
CR + Local treatment	Complete pharmacological response and with local treatment
CR investigator	Complete response: disappearance of all measurable lesions according to investigator's criteria in at least 2 consecutive CT scans
CRF	Case Report Form
CT scan	Computerised axial tomography
CTCAE version 4	Common Terminology Criteria (Common Terminology Criteria for Adverse Events, version 4) of the U.S. Department of Health and Human Services
CVA	Cardiovascular Accident (Stroke)
DMP	Data management plan
DOR	Duration of Response
DOR Duration of Complete Response (CR)	Duration of complete response (CR) to sunitinib; date from the first Computerised axial tomography (CT) scan in which CR was detected to the CT scan in which there was disease progression. If CR continues, continuous CR must be indicated.
DP	Disease Progression
ECOG	Eastern Cooperative Oncology Group. Scale to measure the quality of life of oncology patients with scores running from 0 to 5
eCRF	Electronic Case Report Form
EDP	Exposure during pregnancy
FDA	Food & Drug Administration
GCP	Good Clinical Practice

HFS	Hand-Foot Syndrome
IC	Informed Consent
ICH	International Conference on Harmonisation
IEC	Independent Ethics Committee
KPS	Karnofsky Performance Scale. Scale to quantify the general well-being of patients with cancer and activities of daily living
LDH	Lactate Dehydrogenase
mRCC	Metastatic Renal Cell Carcinoma
mTOR	Mammalian Target of Rapamycin
N/L Ratio	Neutrophil/lymphocyte ratio
NIS	Non-interventional study
ORR	Objective Response Rate
OS	Overall Survival
PFS	Progression-Free Survival
PR	Partial Response

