8.2.2. Exclusion Criteria

Patients who meet any of the following criteria will not be included in the study:

PFIZER CONFIDENTIAL

1. Patients treated with another drug other than Sunitinib.
2. Patients with no radiology reports proving CR.
3. Patients with no record of the dose and regimen received with Sunitinib.
4. Patients who achieved complete remission after 30 October 2018.

Variables

ECOG	Eastern Cooperative Oncology Group	Risk groups
Age of the patient at the time of diagnosis	Epidemiological data	Years
TNM stage (T describes the size of the tumor and the spread of the cancer to nearby tissue; N describes the spread of the cancer to the nearby lymph nodes and the letter M describes the metastases)	Epidemiological data	Tumor stage
Histology of the tumor	Epidemiological data	Pathological anatomy
Tumor Fuhrman grade	Epidemiological data	Pathological anatomy
KPS	Karnofsky Performance Status	Risk groups
Previous nephrectomy	Epidemiological data	Surgery
Cardiac, renal, endocrine, autoimmune and hepatic comorbidities.	Epidemiological data	Disease data
Risk group classification	Epidemiological data	Risk groups
Baseline status of the patient	Epidemiological data	Risk groups
Time from nephrectomy to the start of systemic treatment	Epidemiological data	Risk groups
Hemoglobin	Epidemiological data	Risk groups
Calcium correction	Epidemiological data	Risk groups
LDH levels	Epidemiological data	Risk groups
Lymphocytes	Epidemiological data	Risk groups
Platelets	Epidemiological data	Risk groups

PFIZER CONFIDENTIAL

Neutrophil/lymphocyte index at baseline and after 6 weeks of treatment, at 3 months, at 6 months, at 9 months, at 12 months and then every 6 months	Epidemiological data	Risk groups
Number of metastases	Disease data	Disease data
Number of organs with metastasis	Disease data	Disease data
Median time with treatment before reaching the CR	Treatment data	Disease data
Median duration of the CR	Treatment/disease data	Disease data
Reason why CR ends: progression, tumor stabilization or intolerable toxicity	Disease data	Disease data
Doses and schemes of Sunitinib	Treatment data	Treatment data
Temporary treatment interruptions	Treatment data	Treatment data
Definitive treatment interruption after reaching CR	Treatment data	Treatment data
Active participation of the patient in the decision to definitively interrupt the treatment once the CR has been reached	Patient empowerment	

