Time in Sunitinib treatment once the CR has been reached	Treatment data	Treatment data
Local treatment techniques of residual lesions	Treatment data	Treatment data
PA (pathological anatomy) of metastasectomy: histology and degree of necrosis	Disease data	Disease data
Adverse effects related to Sunitinib treatment of the highest degree achieved	Treatment data	Treatment data
Serious side effects (SAEs) during Sunitinib treatment	Treatment data	Treatment data
Pharmacological group of 2nd line treatment after disease	Treatment data	Treatment data

PFIZER CONFIDENTIAL

progression after a period of time in CR (TKI, mTOR, Immunotherapy)		
Cause of death	Disease data	Disease data

For this observational study, demographic variables that do not imply personal data with which the patient can be identified will be recorded, medical history including date and stage of the disease at diagnosis and progression, surgical treatment, histology, risk criteria for the disease before of its onset, comorbidities, blood and biochemical hematimetry, history of Sunitinib treatment, associated adverse events, clinical efficacy, dose, date of onset and subsequent treatments, as well as the patient's condition (alive, deceased), and date of last contact.

A full description of the variables, including the definitions, will be detailed in the Statistical Analysis Plan of the study. **Source documents**

The investigator will have full responsibility for the accuracy and authenticity of the clinical and laboratory data included in the CRFs at all times.

The source document of this study will be the patient's medical records in their clinical history, including their surgical records that will be kept at the centre where the study is conducted. All data will be captured in a CRF.

If special problems and/or questions arise or governmental requirements to carry out an inspection, it will be necessary to access, in addition, to the complete file of the study, as long as the right to anonymity of the patients is protected.

The information collected in the CRFs must match the data from the medical records.

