8.7. Data analysis

The details of the methodology for the summary and statistical analysis of the data collected in this study will be documented in the Statistical Analysis Plan (SAP), will be archived, and maintained by the sponsor. The SAP can modify the plans originally described in the protocol; any major changes to the definitions of the primary objective of the study or its analysis will be reflected as an amendment to the protocol.

The data will be analysed using descriptive statistics. A statistical summary will be provided including sample size, mean, standard deviation, median and range for continuous variables when applicable; frequency and percentages for categorical variables. Depending on the results of interest, a stratified analysis of the data can be carried out.

Additional exploratory analyses will be developed, such as the neutrophil/lymphocyte index of the patients and additional analyses if required.

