5.4 COVARIATES

All the covariates have been collected on the paper CRF designed for this study as specified in the study protocol.

Variable	Role	Operational definition
ECOG	Epidemiological datum (covariate)	Risk groups
Patient age at time of diagnosis	Epidemiological datum (covariate)	Age
TNM tumour stage (T describes the size of the tumour and the spread of the cancer to nearby tissue; N (nodes) describes the spread of cancer to nearby lymph nodes and M stands for metastases)	Epidemiological datum (covariate)	Tumour staging
Tumour histology	Epidemiological datum (covariate)	Pathological Anatomy
Fuhrman tumour grade	Epidemiological datum (covariate)	Pathological Anatomy
KPS	Epidemiological datum (covariate)	Risk groups
Previous nephrectomy	Epidemiological datum (covariate)	Surgery
Cardiac, renal, endocrine, autoimmune and hepatic comorbidities.	Epidemiological datum (covariate)	Disease data
Classification of the prognostic risk group	Epidemiological datum (covariate)	Risk groups
Patient baseline status	Epidemiological datum (covariate)	Risk groups
Time elapsed from the nephrectomy to the start of systemic treatment	Epidemiological datum (covariate)	Risk groups
Haemoglobin	Epidemiological datum (covariate)	Risk groups
Corrected calcium	Epidemiological datum (covariate)	Risk groups
LDH levels	Epidemiological datum (covariate)	Risk groups
Lymphocytes	Epidemiological datum (covariate)	Risk groups
Platelets	Epidemiological datum (covariate)	Risk groups
Baseline Neutrophil/Lymphocyte rate and at 6 weeks of treatment, 3 months, 6 months, 9 months, 12 months and then every 6 months.	Epidemiological datum (covariate)	Risk groups

PFIZER CONFIDENTIAL

Variable	Role	Operational definition
Number of metastases	Disease data (covariate)	Disease data
Number of organs with metastases	Disease data (covariate)	Disease data
Time on treatment before reaching CR	Secondary objective	Disease data
Duration of CR	Secondary objective	Disease data
Reason why CR ends: progression, tumour stabilisation or intolerable toxicity	Disease data (covariate)	Disease data
Dosage and regimens of Sunitinib	Treatment data (covariate)/Secondary objective	Treatment data
Temporary treatment interruptions	Treatment data (covariate)	Treatment data
Definitive interruption of treatment after reaching CR	Treatment data (covariate)	Treatment data
Active patient participation in the decision to interrupt the treatment definitively once CR is obtained	Patient empowerment (covariate)/Secondary objective	

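### Duration of CR ends at a toxicity-driven treatment change although it is described as disease-free time, and no listed post-CR outcome isolates relapse

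*SAP*

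**What the plan says.** The end of a complete response is described in several places.

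- **Protocol 1, DOR entry:** DOR runs from the first scan showing CR "to the CT scan in which there was disease progression. If CR continues, continuous CR must be indicated". Progression is the only end point.
- **Protocol, Variables table (after 8.2.2):** "Reason why CR ends: progression, tumor stabilization or intolerable toxicity". SAP 5.4 repeats this: "Reason why CR ends: progression, tumour stabilisation or intolerable toxicity".
- **SAP 5, DOR:** the end is the progression scan, "the change of treatment due to unacceptable toxicity, death from any cause or until the date of the last follow-up". The next sentence gives the meaning: "It represents the time that the patient survives without signs of disease".
- **SAP 5, TTP:** from documented CR "until the first day that objective tumour progression, if any, is observed".
- **SAP 7.2.4, Kaplan-Meier outcomes:** the events of interest include progression, toxicity-driven treatment change and death. Three outcomes follow: time to CR, DOR (named without a definition), and PFS, a composite of progression, toxicity change and death that starts at the second CT scan and has a stated censoring rule. TTP is not among them.
- **SAP 7.2.4, Cox model:** the outcome is given as CR/PFS. The covariates include dose, regimen and type of treatment. The hazard ratio is described as relating to time to remission or to disease progression, and the results are meant to support strategy recommendations.

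The protocol leaves definitions to the SAP: "A full description of the variables, including the definitions, will be detailed in the Statistical Analysis Plan of the study". Protocol 8.7 adds: "The SAP can modify the plans originally described in the protocol".

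**The concern.** Median duration of CR is a named secondary objective, and the registry exists to inform what is done after CR. Two things are at stake.

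First, a DOR that ends when a patient in remission changes treatment for toxicity measures relapse, death and tolerability together. Reported as time without signs of disease, it would understate how long remissions last.

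Second, the same composite is labelled PFS and goes into a Cox model with dose and regimen as covariates. If a regimen alters the rate of toxicity-driven change and leaves relapse untouched, the hazard ratio still moves. A reader told that it concerns disease progression would draw the wrong conclusion. The study is descriptive and no hypothesis is tested, so the harm is to the interpretation of the estimates.

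**Working it through.** The plan gives no figure to reproduce, so the first check is of the text.

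**What ends the interval**

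| Place | Progression | Stabilisation | Toxicity | Death | Last follow-up |
|---|---|---|---|---|---|
| Protocol 1, DOR | yes | no | no | no | recorded as continuous CR |
| Protocol Variables table; SAP 5.4 | yes | yes | yes | no | not mentioned |
| SAP 5, DOR | yes | no | yes | yes | in the same list |
| Protocol 7.2 and SAP 5.1, time-from-CR objective | yes | yes | yes | yes | not mentioned |
| SAP 7.2.4, PFS | yes | no | yes | yes | censored |
| SAP 5, TTP | yes | no | no | no | not mentioned |

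1. The abbreviation entry, the variable tables and the SAP 5 definition give three different lists. Of these, death appears only in SAP 5 and stabilisation only in the variable tables.
2. SAP 5 does not say which ends of DOR are events. SAP 7.2.4 names toxicity change and death as events of interest and does not name last follow-up. The natural inference is that the first two are events and last follow-up is censored, but this is not written for DOR.
3. On that reading, the DOR and PFS rows have the same end points. Only the start differs: CR identified, or CR confirmed on the second scan. Protocol 7.2 and SAP 5.1 list them as separate objectives.
4. The only post-CR outcomes in the Kaplan-Meier list are then two versions of one composite. TTP, the measure limited to progression, is defined but not listed.
5. The SAP's own comparison figure, a 27.6-month median from CR in the Czech registry (SAP 2), was defined as relapse or death. The SAP's PFS is not like for like with it.

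**Illustration of size**

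The documents give no rate of toxicity-driven change after CR. Assume constant, independent hazards, and let s be the share of DOR events that are toxicity changes (assumed 5%, 10%, 20%). If h is the hazard without toxicity change, the composite hazard is h/(1 − s), so the composite median is M × (1 − s).

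- M = 27.6 months: 27.6 × 0.95 = 26.2; × 0.90 = 24.8; × 0.80 = 22.1.
- M = 7.9 months (relapse after CR on a TKI alone in the single-hospital series, SAP 2): 7.5, 7.1, 6.3.

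For a covariate that multiplies the toxicity-change hazard by k and leaves progression alone, the composite hazard ratio is 1 + s(k − 1), with s taken in the reference group. With k = 2 (assumed) it is 1.05, 1.10 or 1.20.

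The nearest counts in the documents are the Czech registry's 8 toxicity stops and 18 progression stops. As a crude hazard ratio, r = 8/18 = 0.444 gives 27.6/1.444 = 19.1 months. Those are reasons for stopping, not treatment changes or post-CR hazards, so this shows only that the assumed shares are not an upper bound.

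For scale, with 90 uncensored patients and an exponential 27.6-month median, the density at the median is ln 2/(2 × 27.6) = 0.01256. The 95% half-width is 1.96/(2 × √90 × 0.01256) = 8.2 months.

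**The case against.** Most of the operative text agrees that toxicity can end a CR: both variable tables, the SAP 5 definition and the events named in SAP 7.2.4. The outlier is an abbreviation-list entry. The overlap of DOR and PFS is redundancy. TTP is not a named objective, and time to treatment change and time to death are also left off the list. The illustrated shifts for the 27.6-month median (1.4 to 5.5 months) are smaller than the sampling error above.

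Much of this stands, and it rules out three stronger readings that a reader might infer.

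- **That the SAP breaches the protocol.** It does not. The protocol hands definitions to the SAP and allows it to modify plans.
- **That two programmers would report different medians.** No passage censors toxicity change, and SAP 5 and 7.2.4 together point one way. What is missing is an explicit sentence for DOR.
- **That toxicity change must be removed from DOR.** The variable tables support keeping it. Which definition to adopt is for the authors, provided that it matches its description.

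The objection leaves three things unanswered: the mismatch between DOR and its stated meaning, the lack of any listed post-CR outcome that isolates relapse, and a Cox hazard ratio described as concerning progression when its outcome includes toxicity change. Sampling error does not excuse them, because a shift caused by the definition stays however many patients are included.

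**Conclusion.** The point holds. The documents disagree on what ends a CR, and the SAP's DOR contradicts its own description. On the natural reading, neither the Kaplan-Meier list nor the post-CR Cox outcome separates relapse from tolerability. Severity is minor to moderate, and confidence is moderate.

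The size is not established. The fall from 27.6 months to 26.2-22.1 rests on assumed shares of 5-20%, constant independent hazards, and a median borrowed from another cohort. With the 7.9-month median the same shares move it by only 0.4 to 1.6 months. None of these figures predicts what the registry will find.

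**What to change.** 1. In SAP 7.2.4, add a Kaplan-Meier outcome from the first CR scan to progression or death, censored at last follow-up. List TTP as SAP 5 already defines it.
2. Keep the composite of progression, toxicity change and death, but under a name other than PFS. Time to treatment failure would serve; TTF is already in the protocol's abbreviations.
3. Name the Cox outcome, and use progression or death wherever the hazard ratio is described as concerning disease progression.
4. State the events and censoring for DOR, and reconcile Protocol 1, the Variables table, SAP 5 and SAP 5.4, including stabilisation and death. If toxicity change stays as an event, delete the sentence describing DOR as time without signs of disease.
5. As a sensitivity analysis of the progression-or-death outcome, censor at the sunitinib end date when the recorded reason is toxicity. The visible CRF list in SAP 5 shows no start date for later treatment (one item is redacted), so the sunitinib end date is the usable one.

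The cost is SAP wording and one or two extra curves, from dates already listed in SAP 5: progression, death, and sunitinib end date with reason. The downside is that the progression-or-death outcome may include remission time on a later drug. The sensitivity analysis gives an indication of how much that matters, under the assumption that censoring at a toxicity stop is independent of relapse. No planned output is lost.
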